## **2. Research objectives**

Main objective: the efficacy (rate of change in renal function GFR, overall survival OS, tumor-free survival TFS, progression-free survival PFS, etc.) and safety (positive incision margin rate, intraoperative blood loss, postoperative complication rate, etc.) of unassisted zero-ischemia enucleation in the surgical treatment of patients with early stage (T1) renal cancer.

Secondary objectives: differences between unassisted zero ischemic enucleation of renal cancer and partial nephrectomy with clamping of the hilum in the surgical management of patients with renal cancer and the role of the modified ABC score in the assessment of renal cancer.

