## **3. Study content and design**

This study aims to evaluate the effectiveness and safety of the surgery by using renal cancer patients who met the inclusion criteria. Summarizing the preoperative, perioperative, and postoperative data, and evaluating the operative time, intraoperative bleeding, postoperative hospitalization days, postoperative complication rate, postoperative short-term, intermediate, and long-term renal function indexes, overall survival, tumor-free survival, progression-free survival and postoperative renal cancer recurrence rate of the patients.

Statistical software is used to describe the characteristics of patient data. T-test, rank sum test, multi-factor regression, and cox regression are used to investigate the effects of each factor on the treatment outcome and prognosis of patients undergoing zero-ischemic renal enucleation, to describe whether there are differences in the safety and efficacy of zero ischemic renal enucleation compared with traditional

partial nephrectomy for the treatment of stage T1 renal carcinoma.

This study used a retrospective research trial design to include 73 patients who underwent zero-ischemic enucleation and 73 patients who underwent traditional partial nephrectomy from 2014 to 2022, for a total of 146 patients. The formula for calculating the sample size is as follows.

$$n = [z_{\alpha}\sqrt{2\bar{p}\bar{q}} + z_{\beta}\sqrt{p_0q_0 + p_1q_1}]^2 p / (p_1 - p_0)^2$$

Figure 1. Estimated sample size calculation

note:  $Z_{\alpha}$ 、 $Z_{\beta}$  are the quartiles under standard normal distribution.

$p_1$ : Expected morbidity in the exposed group.

$p_0$ : Expected incidence in the control group.

$q_1$ :  $q_1 = 1 - p_1$ .

$q_0$ :  $q_0 = 1 - p_0$ .

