## **5. Experimental program**

**5.1** The patients are screened according to the inclusion and exclusion criteria. Then the patients are divided into two groups according to whether they underwent zero-ischemic enucleation or partial nephrectomy, with the zero-ischemic enucleation group as the test group and the partial nephrectomy group as the control group. Describing the preoperative conditions (age, sex, Anatomy of tumor, RENAL score, ABC score, preoperative renal function), the perioperative conditions (operation time, intraoperative bleeding, perioperative complications, negative/positive specimen margins, postoperative renal function changes, postoperative hospitalization days), and the postoperative condition (follow-up renal function, tumor recurrence rate, overall survival, tumor-free survival, progression-free survival).

**5.2** The data of the two groups are corrected for baseline and screened so that there is no statistical difference in the number of patients, gender age, tumor anatomy, renal function and other preoperative conditions between the two groups (t-test/rank sum test  $p > 0.05$ ).

**5.3** The zero ischemic renal enucleation group is grouped according to RENAL score, ABC score and other scoring criteria. Different preoperative tumor score groupings are used as exposure

factors, and the percentage decrease of postoperative renal function compared with preoperative, perioperative complication rate and postoperative survival rate are used as outcome variables to analyze the association between exposure factors and outcome, to investigate the association of different factors on the surgical outcome of zero ischemic renal enucleation.

**5.4** Using zero-ischemic nephrectomy or partial nephrectomy with clamping of the renal hilum as the exposure factor. T-test/rank sum test and one-way regression are used to compare the efficacy indexes such as negative/positive tumor margins, postoperative and follow-up renal function, survival rate, and safety indexes such as perioperative complication rate and intraoperative bleeding between the two groups to investigate whether there is a statistical difference in their treatment safety and efficacy. Then we investigated whether there are statistical differences and correlations between the safety and efficacy of the treatment, and whether there are statistical differences in survival outcomes between the two groups by multifactorial cox regression.

[figure not shown]

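### Balance between the two non-randomised groups is judged by baseline p > 0.05 with no correction method named in the text, and renal function, blood loss and complications are then assigned unadjusted tests

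*Combined protocol and SAP*

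**What the plan says.** Section 3 describes a retrospective design that will "include 73 patients who underwent zero-ischemic enucleation and 73 patients who underwent traditional partial nephrectomy from 2014 to 2022". Section 5.1 forms the groups by the operation each patient had.

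On comparability, section 5.2 states: "The data of the two groups are corrected for baseline and screened so that there is no statistical difference in the number of patients". It goes on to name sex, age, tumour anatomy, renal function and other preoperative conditions, with t-test or rank sum p > 0.05 as the criterion. Section 6.3 adds baseline tests at the 5% level. Neither section names matching, weighting, stratification or regression as the correction, and neither gives another measure of balance.

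On the analysis, two sections differ:

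- Section 3: "T-test, rank sum test, multi-factor regression, and cox regression are used to investigate the effects of each factor on the treatment outcome and prognosis". The stated purpose includes "to describe whether there are differences in the safety and efficacy of zero ischemic renal enucleation compared with traditional" partial nephrectomy. The target is generic, and no covariates are listed.
- Section 5.4: "T-test/rank sum test and one-way regression are used to compare the efficacy indexes". The list that follows covers margins, renal function, survival rate, complications and bleeding. Multifactorial Cox regression is then named for survival outcomes, also without covariates.

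Renal function is described in three ways: section 2 has "the efficacy (rate of change in renal function GFR", section 5.3 has "the percentage decrease of postoperative renal function compared with preoperative", and section 5.4 refers to postoperative and follow-up renal function.

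**The concern.** With groups formed by the operation received, confounding is the main threat to the comparison. A baseline p-value does not measure balance, because it depends on sample size as well as on the gap. In samples of this size a gap large enough to matter can easily be non-significant, and dropping patients makes p > 0.05 easier to reach without making the groups more alike.

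Whatever measured imbalance passes the rule then enters the t-test, rank sum test or single-factor regression, where it can be read as an effect of the operation. The reader of the results could not tell how much remains. That depends on the unnamed correction, on how strongly the covariates predict outcome, and on whether the imbalances act in the same direction. The p > 0.05 rule shows none of these.

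**Working it through.** **The plan's own figure.** Section 3 gives 73 per group and a formula, but no values for p0, p1 or power. The figure can be neither reproduced nor refuted; for example, 0.10 vs 0.28 at 80% power and two-sided 5% gives about 73, as do many other pairs. I take 73 + 73 as given.

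**Step 1. What p > 0.05 accepts.** Inputs: n = 73 per group (section 3) and two-sided 5% (section 6.3).

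- Continuous covariate: largest accepted observed gap = t(0.975; 144 df) × √(2/73) = 1.9766 × 0.1655 = **0.327 SD**.
- Binary covariate: 36/73 vs 47/73 (49% vs 64%) gives chi-square 3.38, p = 0.066, and passes. 36/73 vs 48/73 gives p = 0.045 and fails. The rule therefore tolerates about 15 percentage points.

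**Step 2. How often a true gap passes.** Noncentral t with noncentrality d × √(73/2):

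| True gap d | Noncentrality | Chance that p > 0.05 |
|---|---|---|
| 0.20 SD | 1.208 | 77.5% |
| 0.30 SD | 1.812 | 56.3% |

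For three independent covariates, the chance that all pass is 0.775³ ≈ 47% at 0.20 SD and 0.563³ ≈ 18% at 0.30 SD.

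Steps 1 and 2 need nothing beyond n and alpha. Steps 3 to 5 rest on assumptions, because the documents give no covariate-outcome correlations.

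**Step 3. Illustration with no correction step.** This is not the plan as written, since 5.2 does promise a correction. Assumed: three independent measured covariates, each shifted 0.20-0.30 SD, no treatment effect, a continuous outcome, and covariates explaining 10-40% of outcome variance (R²). Simulated datasets were kept only if all three baseline tests gave p > 0.05.

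| Pattern | Unadjusted type I error | Remaining bias |
|---|---|---|
| One prognostic covariate | about 5-8% | 0.04-0.12 SD |
| Three, same direction, R² 10% | about 7-8% | 0.07-0.10 SD |
| Three, same direction, R² 40% | about 12-19% | 0.15-0.20 SD |
| Three, one acting in reverse | about 4-5% | 0.02-0.07 SD |

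The 19% needs all three shifted by 0.30 SD in the same direction at R² 40%, and only 18% of such datasets pass all three checks. Covariate-adjusted models held 3.9-5.6%, as they must when every confounder is measured.

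**Step 4. Illustration with an assumed correction.** 1:1 propensity matching, R² 40%, shifts of 0.20 / 0.30 SD in the same direction:

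| Control pool | Remaining bias (SD) | Unadjusted type I error |
|---|---|---|
| 3:1 | 0.008 / 0.018 | 1.6% / 1.5% |
| 1.5:1 | 0.049 / 0.095 | 2.6% / 5.7% |

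**Step 5. Precision when balance is good.** Adjusted variance ≈ (1 − R²) × unadjusted variance. At R² of 10, 20 and 40% the unadjusted analysis carries 10, 20 and 40% of its variance unnecessarily.

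**The case against.** The strongest reply is that 5.2 says the data are corrected, so error rates computed with no correction do not describe this plan. Equal groups of 73 are at least compatible with 1:1 matching, and under that assumption the unadjusted test runs at 1.5-5.7%, mostly on the conservative side. This stands: step 3 is an illustration, not an estimate for this study. It does not rescue the p-value as a balance measure, and it does not supply the missing name of the method.

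A second reply is that adjusted analysis is under-specified, not absent. Section 3 does link multi-factor regression to treatment outcome and to the safety and efficacy comparison, and the sentence in 5.4 after the single-factor tests could describe a univariable-then-multivariable sequence. This also stands, so a reader who infers that no adjusted analysis is planned outside survival goes too far. But the only methods 5.4 clearly attaches to these endpoints are unadjusted, so sections 3 and 5.4 need reconciling.

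Other stronger readings are not supported:

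- That patients are removed repeatedly until p exceeds 0.05. The text states an aim, not an iterative procedure.
- That the gap between the nearly 100 zero-ischemia cases in section 1 and the 73 included shows unexplained selection. The former is a statement of experience, not limited to eligible patients, and sections 4 and 5.1 do give a route.
- That the three renal-function descriptions contradict each other. Rate of change and percentage decrease may be one quantity, 5.3 concerns the enucleation group only, and 5.4 may just be naming time points.
- That a baseline GFR gap biases a change score by a known amount. That requires both groups to share one regression line on baseline, which non-randomised data do not guarantee.

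**Conclusion.** The concern holds in a limited form. At 73 per group, p > 0.05 does not establish balance; this follows from the sample size alone. The text names no correction method, and it clearly assigns only unadjusted methods to renal function, blood loss and complications. Figure 2 might name a method, but 5.2, 5.4 and 6.3 would still need to state it.

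The size of any residual bias cannot be derived from the documents. Under the stated assumptions the consequence runs from none, or a conservative test, through modest inflation with one prognostic covariate, to substantial inflation only in the extreme three-covariate case without correction. Loss of precision remains even with good balance. This should be fixed, but it is not evidence that the comparison is invalid.

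**What to change.** 1. **Sections 5.2 and 6.3.** Replace the p > 0.05 criterion. Suggested content: balance is reported as standardised mean differences; the baseline correction, if any, is named together with its variables; no patient is removed to reach a p-value; and counts are given from all eligible patients to the 73 + 73, with reasons for exclusion.
2. **Section 5.4, with one sentence in section 3.** Make the main between-group comparison of renal function, blood loss and complications covariate-adjusted, also after any matching, and state that this is the multi-factor regression of section 3.
   - Covariates: preoperative GFR, age, sex, RENAL score and T1a/T1b. Section 5.1 lists the patient and tumour variables, and section 4.1 requires the stage.
   - Renal function: one stated measure, used in sections 2, 5.3 and 5.4.
   - Complications: a low-dimensional adjustment such as a single propensity score. At an assumed rate of 10-20%, 146 patients give only about 15-29 events (146 × 0.10 = 14.6; 146 × 0.20 = 29.2).
   - Margins: Fisher's exact test, labelled unadjusted.
   - The planned unadjusted tests stay as supportive analyses.
3. **Limitations.** State that baseline adjustment of GFR rests on its own assumption in non-randomised data, and that unmeasured confounding remains whichever model is used.

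Cost: rewording of four places and a little more analysis work, with no change in sample size. Reporting the selection counts may need a look back at records. The adjusted estimates may be less favourable than the unadjusted ones.

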### **6.3 Statistics**

Data entry: Enter the age, gender, kidney cancer stage and prognosis follow-up of the subjects.

Data management: The data are presented by number, and all personnel except the initial data entry personnel do not have access to the subjects' initial information (including subjects' personal information such as subjects' names, addresses, occupations and other sensitive information). There is no direct contact between the data entry personnel and the subjects, and all privacy of the subjects is protected from disclosure.

All hypothesis tests are two-sided, and differences are considered statistically significant at  $P < 0.05$ . Baseline data are evaluated for comparability between groups, and two-tailed statistical tests are performed at the  $\alpha=5\%$  level. The chi-square test or Fisher's exact probability method is used for comparison between groups for count data, the t-test for comparison between groups for measurement data, and the rank sum test for comparison between groups for nonparametric variables.

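### Section 5.3 makes unspecified groupings of the tumour scores the exposure among 73 enucleation patients, fixing no cut points and no use of the scores' order; an ordinal or trend analysis would be the better primary test

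*Combined protocol and SAP*

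**What the plan says.** Section 2 of the combined protocol and SAP lists among its secondary objectives "the role of the modified ABC score in the assessment of renal cancer". Section 5.3 is where tumour scores are related to outcome. It says that "The zero ischemic renal enucleation group is grouped according to RENAL score, ABC score and other scoring criteria" and then that "Different preoperative tumor score groupings are used as exposure" factors. For the outcomes, "the percentage decrease of postoperative renal function compared with preoperative, perioperative complication rate and postoperative survival rate are used as outcome variables".

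The group concerned has 73 patients. Section 3: "This study used a retrospective research trial design to include 73 patients who underwent zero-ischemic enucleation and 73 patients who underwent traditional partial nephrectomy". Section 3 also lists multi-factor regression and Cox regression for the effect of factors on outcome in enucleation patients, but does not say in what form a score enters. Section 6.3 names chi-square or Fisher, the t-test and the rank sum test for comparing groups, two-sided at 5%. It names no trend test.

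No section gives the number of score groups, the cut points, whether the order of the groups is used, or the expected strength of association. Sections 5.1 and 5.3 refer to the ABC score, while section 2 refers to the modified ABC score.

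**The concern.** A complexity score is ordered. Once it is cut into groups, differences within a group are discarded. If the groups are then compared without regard to order, the direction of the association is discarded too. With 73 patients there is little information to spare.

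The second issue is the freedom to choose. The protocol is dated February 2023 and the operations ran from 2014 to 2022, so the perioperative results already exist. Cut points fixed only at analysis can be chosen, knowingly or not, because they give a small p-value. The open-ended reference to other scoring criteria widens that choice.

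At stake is whether a finding on a stated secondary objective, positive or negative, can be trusted.

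**Working it through.** **The plan's own figure.** The only sample-size figure is 73 per group for the comparison of the two operations. Section 3 prints a two-proportion formula but gives no values for the expected proportions or the power. Many inputs return about 73: for example, two-sided 5%, 80% power and no continuity correction give it for 0.10 against about 0.28, or for 0.30 against about 0.525. The figure can be neither confirmed nor refuted, and no power is stated for the score analysis.

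**Inputs.** From the documents: n = 73, two-sided α = 0.05. Assumed, because the documents give nothing: a continuous renal-function outcome, a linear association, a roughly normal score, and correlation r between 0.25 and 0.35.

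**Step 1, ungrouped score.** Power ≈ Φ(arctanh(r)·√(n − 3) − 1.96). For r = 0.30: arctanh(0.30) = 0.3095; × √70 (8.367) = 2.590; − 1.960 = 0.630; Φ = 74%.

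**Step 2, grouped score.** Grouping multiplies r by a factor f.

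- Two groups with share q below the cut: f = φ(z_q)/√(q(1 − q)). At the median f = 0.798, so r becomes 0.239; 2.042 − 1.960 = 0.082; power 53%. Since f² = 2/π = 0.64, this is like using about 46 of the 73 patients (0.64 × 73 = 46.5).
- An 80/20 split: f = 0.700, r becomes 0.210; 1.783 − 1.960 = −0.177; power 43%.
- Three equal groups scored in order: f = 2φ(0.431)/√(2/3) = 0.891, r becomes 0.267; 2.291 − 1.960 = 0.331; power 63%.

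The unordered three-group ANOVA was simulated.

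| Analysis | r = 0.25 | r = 0.30 | r = 0.35 |
|---|---|---|---|
| Ungrouped score | 57% | 74% | 86% |
| Three equal groups, trend | 47% | 63% | 77% |
| Median split | 39% | 53% | 67% |
| Three groups, ANOVA (simulated) | 38% | 53% | 68% |
| 80/20 split | 32% | 43% | 55% |

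Simulation agrees within about two points; at r = 0.30 it gives about 54% for the median split and about 64% for the three-group trend test.

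**Step 3, how far the loss can vary.** Take r = 0.323, where the ungrouped score has 80% power.

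- A 90/10 split leaves 36%, a loss of 44 points.
- Four equal groups with a trend test leave about 75%.
- For an assumed four-level score with 25%, 35%, 25% and 15% of patients per level, using the levels in order keeps 80%. Splitting the top two from the bottom two gives 69%, the lowest level against the rest 54%, and ANOVA on the four levels 64%.

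The loss thus runs from nil to about 44 points, depending on choices that section 5.3 leaves open.

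**Step 4, free cut points.** Suppose there is no association and the best of three cuts (lower tertile, median, upper tertile) is reported. Three independent tests would give 1 − 0.95³ = 14.3%. The cuts overlap: the correlation between cuts at q₁ < q₂ is √[q₁(1 − q₂)/((1 − q₁)q₂)], which is 0.71 for a tertile with the median and 0.50 for the two tertiles. With these correlations the false-positive rate is 11.4%; simulation at n = 73 gives 11–12%. This is for one score and one outcome, whereas section 5.3 has at least two scores and three outcomes.

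Complications and survival cannot be worked through: no complication rate or event count is given.

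**The case against.** The strongest reply is that section 5.3 does not commit the study to an inefficient test. It speaks of analysing association and names no method, and section 3 already plans regression and Cox models for enucleation patients. Grouping by a score may mean using the score's own levels, and ordered levels could enter as a trend term. That reply stands in part: what is shown is an unspecified analysis, not a decided choice of unordered comparison. But the only text that defines the form of the exposure says groupings, regression on unordered groups loses the same information, and no passage brings the order in.

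It can also be said that score classes are customary. They can still be tabulated while the test uses the ordered score. The documents themselves define no classes.

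Two stronger readings are tempting and should be resisted. A reader might infer that the plan forfeits about 20 points of power for the score objective. The documents do not support that: the figure belongs to a median split or unordered ANOVA with r near 0.3, on the renal-function outcome only, and the objective names only the modified ABC score, whose number of levels is not given. A reader might also infer that a real association is likely to be missed. At r = 0.30 the median split and ANOVA still have slightly more than even power, and at r = 0.25 the ungrouped score has only 57%.

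For survival, scarcity of events may matter more than score coding. Section 1 reports no local recurrence in over 500 enucleations by the same team, so a per-point Cox model in 73 T1 patients may not be estimable.

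**Conclusion.** The point holds as one of underspecification with a better method readily at hand. Section 5.3 makes groupings the exposure in 73 patients and fixes neither their number, the cut points nor the use of order.

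The loss of power is conditional. Under a linear association with r about 0.30, it is about 20 points for a median split or unordered three-group ANOVA, about 10 for a three-group trend test, and nil if the score's own levels are used in order. The inflation of the false-positive rate from 5% to about 11–12% does not depend on the assumed correlation, but it does assume that three cuts are tried and the best one reported. Nothing in the documents shows that this will happen; nothing prevents it either. Neither size carries over to complications or survival.

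**What to change.** In section 5.3:

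- Make the primary test of each score an ordinal term, reporting the effect per point or level with a 95% confidence interval, or use a 1-df trend test.
- Use linear regression for renal function, logistic regression for complications, and Cox regression for survival only if the number of events supports it.
- Show score classes descriptively only, with cut points fixed before analysis.
- Reconcile the modified ABC score of section 2 with the ABC score of sections 5.1 and 5.3.

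The cost is SAP wording, with no new data. The one drawback is that linearity across the score is assumed; the descriptive summary by class gives a check on it.

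### The between-arm comparison of renal function in section 5.4 is not adjusted for preoperative GFR, and the p > 0.05 screen in 5.2 does not make up for that

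*Combined protocol and SAP*

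**What the plan says.** Section 2 puts "rate of change in renal function GFR" first among the efficacy measures of the main objective. It names no single primary endpoint and no time point.

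The between-arm analysis is in 5.4: "T-test/rank sum test and one-way regression are used to compare the efficacy indexes such as negative/positive tumor margins, postoperative and follow-up renal function". The one multivariable model that 5.4 ties to an outcome is for survival: it asks "whether there are statistical differences in survival outcomes between the two groups by multifactorial cox regression". Section 6.3 repeats the t-test for measurement data and the rank sum test for nonparametric variables.

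Four other places bear on baseline:

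- 5.1 lists preoperative renal function, age and RENAL score among the data described.
- 5.2 says the two groups are corrected for baseline and screened until preoperative variables, renal function included, differ with p > 0.05. It gives no method for the correction.
- 5.3 takes "the percentage decrease of postoperative renal function compared with preoperative" as an outcome, but only inside one arm: "The zero ischemic renal enucleation group is grouped according to RENAL score, ABC score and other scoring criteria". It names no test.
- Section 3 says "T-test, rank sum test, multi-factor regression, and cox regression are used to investigate the effects of each factor on the treatment outcome and prognosis". It attaches no outcome or covariates to the multi-factor regression.

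**The concern.** The design is retrospective and patients were not randomised, so the two surgical groups may well start from different GFR levels. Preoperative GFR is probably also the best single predictor of postoperative GFR. A comparison that ignores it loses precision and carries part of any baseline gap into the result.

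The screen in 5.2 does not prevent this. A non-significant test means that a gap was not detected, not that it is absent. The plan also leaves open whether 5.4 analyses the postoperative value or a change from baseline. The two respond to a baseline gap in opposite directions, so the sign of the error would depend on a choice not yet made.

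**Working it through.** **Inputs from the documents.** 73 per group, 146 in total (section 3); two-sided 5% level (6.3); balance screen at p > 0.05 (5.2).

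**The plan's own figure.** Section 3 prints a two-proportion formula but no values for p0, p1 or power, so 73 per group can be neither reproduced nor refuted. Several pairs fit; for example 0.15 against 0.35 with two-sided 80% power gives 73. Because it is a formula for proportions, it does not size the GFR comparison. Only the 73 is used below.

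**Assumed.** The documents give no pre/post correlation, so r = 0.5, 0.7 and 0.9 are shown. Pre- and postoperative variances are taken as equal, and results are in SD units of GFR.

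**Step 1: what the screen lets through.** The standard error of a difference in means is √(2/73) = 0.1655 SD. The largest non-significant gap is t(0.975, 144) × 0.1655 = 1.977 × 0.1655 = 0.327 SD.

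**Step 2: variance.** Relative to the postoperative value (1), a change score has variance 2(1 − r) and the baseline-adjusted comparison 1 − r².

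| r | Change score | Adjusted | Adjusted ÷ postoperative | Adjusted ÷ change |
|---|---|---|---|---|
| 0.5 | 1.00 | 0.75 | 75% | 75% |
| 0.7 | 0.60 | 0.51 | 51% | 85% |
| 0.9 | 0.20 | 0.19 | 19% | 95% |

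These ratios leave out a small cost of adjusting when the groups differ at baseline. At the 0.327 SD gap that cost is a factor of 1 + 1.977²/144 = 1.03.

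**Step 3: error at the largest passing gap, no true effect.** If the baseline-adjusted model holds, the postoperative comparison is off by r × 0.327 SD, in favour of the group that starts higher. A change score is off by (1 − r) × 0.327 SD, against that group. Given the gap, the estimate has SD √(1 − r²) × 0.1655, while the test rejects beyond 1.96 × 0.1655 (postoperative value) or 1.96 × √(2(1 − r)) × 0.1655 (change score).

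| r | Postoperative: error (SD) | False positives | Change: error (SD) | False positives |
|---|---|---|---|---|
| 0.5 | 0.16 | 13% | 0.16 | 13% |
| 0.7 | 0.23 | 21% | 0.10 | 10% |
| 0.9 | 0.29 | 34% | 0.03 | 7% |

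Example, r = 0.7, postoperative value: the error is 0.7 × 0.327 = 0.229, the conditional SD is 0.714 × 0.1655 = 0.118 and the threshold is 0.324. The chance of exceeding it is that of a normal deviate above (0.324 − 0.229)/0.118 = 0.81, about 21%.

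**Step 4: half that gap (0.164 SD).** The same formulas give 4.8/3.8/0.7% for the postoperative value and 4.8/4.9/5.0% for a change score: no inflation.

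**Cross-check by simulation.** This used 5,000 runs per case, with an assumed baseline mean of 90, SD 20, mean fall of 10, a gap of 0.32 SD and no effect. Rejection at r = 0.5/0.7/0.9 was 12/19/31% for the postoperative value and 11/7/5% for percentage change. It was about 5% throughout for regression adjusted for baseline, under the model that generated the data.

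**The case against.** A reader might infer that the plan compares the arms on an unadjusted percentage decrease by t-test or rank sum test. The documents do not say so. The percentage decrease is an outcome of 5.3, within the enucleation arm and with no test named. The t-test and rank sum wording is in 5.4, for postoperative and follow-up renal function. The rate of change in section 2 makes a change measure in 5.4 possible but does not state it, which is why both readings are worked above.

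A reader might also infer that the plan rules adjustment out. It does not: 5.2 mentions baseline correction, and section 3 lists multi-factor regression separately from Cox regression. Both remain undefined, though, and 5.4, where the between-arm comparison is set out, assigns neither to renal function. The fair statement is that adjustment is not committed to.

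Two technical objections stand. The false-positive figures are worst cases, conditional on the largest gap that passes; they are not the study's overall error rate. And without randomisation, change score and baseline adjustment rest on different untestable assumptions: if the gap is a stable group difference, the change score is unbiased and the adjusted comparison is not. This weakens any claim that a change score is biased. It does not rescue a postoperative comparison that ignores baseline altogether.

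**Conclusion.** The point holds for 5.4: no baseline-adjusted model is specified for renal function, and the 5.2 screen does not replace one. On the literal wording, which names the postoperative value, the loss of precision grows with r, and adjustment leaves 75% of the variance at r = 0.5 but 19% at r = 0.9. If a change score is meant, the gain is smaller and almost vanishes at r = 0.9. The error from imbalance matters near the limit of the screen and is not a demonstrated bias in this study, since neither the actual gap nor r is given. All sizes rest on 73 per group and equal variances; the error figures also need the baseline-adjusted model to hold. This should be corrected before analysis, but it does not invalidate the study.

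**What to change.** In 5.4, make the main renal-function analysis a linear regression of follow-up GFR (log scale if skewed) on surgery group, with preoperative GFR, age and RENAL score as covariates. Choose the postoperative window from the available records and state it, because section 3 speaks only of short-term, intermediate and long-term renal function. Report the adjusted difference, or ratio on the log scale, with a 95% CI. Keep the percentage decrease as a descriptive summary. State what the baseline correction in 5.2 consists of.

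The same model cannot be carried into 5.3, where every patient had enucleation and RENAL score can be the exposure. There, regress follow-up GFR on score group with preoperative GFR and age, without surgery group, and without RENAL score as a covariate where it is the exposure.

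The cost is small. The covariates are already listed in 5.1, and this is ordinary linear regression. A window must be chosen, and patients without a GFR in it drop out of that analysis, so their number should be reported by arm. Adjustment for these covariates will not remove all confounding, and the report should say so.
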